7.3 CLINICAL PARAMETERS BY VISIT

Initial Screening/Baseline Visit

Potential study participants will be screened for eligibility per the protocol eligibility criteria. The Screening/Baseline visits may be split into two or more days. After informed consent has been signed and washout from previous medications is complete (when necessary), the following assessments will be performed as part of the subject eligibility assessment:

- MINI
- ATHF
- Mini Mental Status Exam (MMSE-2)
- Medical and psychiatric history
- Concomitant medication history
- Adverse Events
- Demographics
- NeoSync EEG
- Vital Signs (HR, BP)
- Weight
- Pregnancy Test (HCG)
- Urine Toxicology Screen
- HAM-D/MADRS
- IDS-SR
- C-SSRS
- Standard 12 lead ECG (optional)
- Physical Examination (optional)
- Laboratory Assessments (optional)

Randomization into the Trial

Upon successful completion of Screening and Baseline visits to establish eligibility, subjects will be randomized into the trial. A PPM will be selected and assigned to the subject. This PPM can only be used with either an active or sham device as they are already encrypted and assigned to a randomization arm per the pre-generated randomization schema. The subject's EEG will be recorded. The EEG will be

processed and used to determine the treatment parameters stored on the subject's PPM. The PPM should be labeled with the Sub ID. That PPM must be used with that device for all treatments.

Double-Blind Treatment Visits (Week 1-6)

After the subject has been deemed to be acceptable for inclusion in the trial and randomized to a treatment group, they may begin scheduled treatments. They will go to the physician's office 5 days per treatment week to complete the treatment procedure. In addition, subjects will be assessed for changes in adverse events, concomitant medications, or worsening of symptoms that may need physician intervention at each of the treatment visits. The first treatment visit may occur after randomization at the baseline visit given sufficient time.

Double-Blind Evaluation Visits (Week 1-5)

In addition to the treatment visits, an evaluation will be conducted on the same day as the last treatment (5th treatment session, within 10 calendar days) of each weekly treatment cycle. The following assessments will be performed as part of that evaluation:

- HAM-D/MADRS
- IDS-SR
- C-SSRS
- Adverse Events
- Concomitant Medications
- Treatment Blinding Questionnaire(s) (Week 1)

Week 6 /Early Termination Visit

If assessments are done as part of an early discontinuation visit, subject should be asked to come in for the post-treatment follow-up visit.

- Vital Signs
- Weight
- HAM-D/MADRS
- IDS-SR
- C-SSRS
- Adverse Events
- Concomitant Medications
- Treatment Blinding Confirmation Questionnaire(s)
- Determination of eligibility for open label sTMS treatment

Open Label Evaluation Visits (Week 7-12)

In addition to the treatment visits, an evaluation visit will be conducted on the last day of each weekly treatment cycle. The following assessments will be performed as part of that evaluation:

- HAM-D/MADRS
- IDS-SR
- C-SSRS
- Adverse Events
- Concomitant Medications

8 DISCONTINUATION

8.1 WITHDRAWAL FROM STUDY

Subjects have the right to withdraw from the study at any time, for any reason, without jeopardizing their medical care. The Investigator, the IRB and NeoSync, Inc. also have the right to withdraw subjects or terminate the trial for the following reasons:

- Occurrence of unacceptable risk to the subjects enrolled in the study, including significant worsening of depression.
- A decision on the part of the Sponsor to suspend or discontinue testing, evaluation, or development of the product.

The Investigator may use the weekly clinical evaluation to determine if the subject's symptoms or quality of life have significantly deteriorated to the point where withdrawal from the study would be in the subject's best interests.

A study conducted at a single study site or a single study site in a multicenter study may also warrant termination under the following conditions:

- Failure of the Investigator to comply with pertinent regulations of appropriate regulatory authorities.
- Insufficient adherence to protocol requirements.
- Submission of knowingly false information from the research facility to the Sponsor, study monitor, or appropriate regulatory authority.

Subjects who withdraw from the study for any reason will not be replaced. Subjects who voluntarily withdraw from the study will be asked to complete the Week 6/Early Termination assessments. Subjects who are withdrawn due to adverse events will be followed until resolution or stabilization of the adverse event.

8.2 REASONS FOR DISCONTINUATION OF SUBJECTS

Subjects may decide to discontinue their participation in the study for various reasons such as unmanageable side effects, lack of efficacy, withdraw of consent, etc. The PI may also decide to withdraw the subject for reasons including: protocol noncompliance, safety concerns, etc.

Sites will attempt to gather information for all subjects that discontinue from the study whenever possible. The sites shall, at minimum, collect details regarding the subject's primary reason for discontinuing, HAM-D, MADRS, current medication use, and adverse events. Other scales may be collected, based upon the subject's availability.

8.3 SUBJECTS LOST TO FOLLOW-UP

In the event that a subject does not return for his/her next scheduled visit, sites must make every attempt to contact the subject to attempt to retain them in the study. Site staff should contact the subjects in order to either continue his/her study participation, or to ensure safe discontinuation from study and transfer care to the subject's personal physician/psychiatrist. Sites will gather as much information as possible for any subject that discontinues his/her study participation. If a subject does not show up for a scheduled visit the site should make the following efforts to continue the subject in the study and/or gather discontinuation status information:

- At least three follow-up phone calls to attempt to contact subject. Documentation of all phone call attempts in the subject's source documentation.
- Phone calls should be made at different times in the day, and different days of the week.
- Send a certified letter to each subject that does not return phone calls.

8.4 SUBJECT STUDY COMPLETION

Any subject who remains in the trial to the endpoint analysis (Week 6 Evaluation Visit) will have final evaluations completed in line with the Week 6 visit schedule of events. Based upon the clinician's assessment of subject's current status (e.g. response, side effect profile, insurance situation), a decision will be made as to the best treatment plan for the subject.

If the subject does not reach a clinical assessment definition of "remission" (HAM-D₁₇ score ≤ 7) by the time of their Week 6 Evaluation Visit, they are eligible to be considered for an additional 6 weeks of open label sTMS treatment. This open label treatment is completely optional and shall be considered based upon the clinician's judgment on the best course of therapy. Alternatively, the subject may begin a course of antidepressant medications or may choose to return to their primary physician for follow-up care. If the subject does participate in the open label sTMS treatment phase, they will be evaluated weekly during the 6 weeks of therapy. Information about the subjects' transition will be collected along with their current symptoms, adverse events, etc. at the final study visit.

9 EVALUATION OF SAFETY

An adverse event (AE) is defined as any untoward medical occurrence in a subject treated with an investigational product that does not necessarily have to have a causal relationship with the treatment under investigation. An AE can therefore be any unfavorable and unintended sign (including abnormal laboratory finding), symptom, or disease temporally associated with the use of an investigational product whether or not considered related to the investigational product.

A Serious Adverse Event (SAE) is defined as an adverse event that results in any of the following outcomes:

- Death
- Is life-threatening
- Requires in-subject hospitalization or prolongation of existing hospitalization
- Persistent or significant disability/incapacity
- A congenital anomaly or birth defect

An unanticipated adverse device event (UADE) is defined as any serious adverse effect on health or safety or any life-threatening problem or death caused by, or associated with, a device, if that effect, problem, or death was not previously identified in nature, severity, or degree of incidence in the protocol and/or Instruction For Use (IFU) or any other unanticipated serious problem associated with a device that relates to the rights, safety, or welfare of the subject.

All adverse events that do not meet any of the criteria for SAEs or UADEs should be regarded as non-serious adverse events.

Progression of disease, in this case major depressive disorder, reflects lack of therapeutic efficacy and should not be treated as serious adverse events. However, other events or complications meeting the criteria for serious adverse events should be considered as a serious adverse event and should be reported immediately to NeoSync regardless of presumed relationship to the investigational device.

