4.2 EXCLUSION CRITERIA

Subjects will be excluded from study participation if one of the following exclusion criteria applies:

1. Subjects are unable or unwilling to give informed consent.
2. Diagnosed with the following conditions (current unless otherwise stated):
 - a. Any other current primary Axis I mood, anxiety, or psychotic disorder, including bipolar disorder.
 - b. Depression secondary to a general medical condition, or substance-induced.
 - c. History of substance abuse or dependence within the past 6 months (except nicotine and caffeine).
 - d. Any bipolar disorder or psychotic disorder (lifetime), including schizoaffective disorder, or major depression with psychotic features in this or previous episodes.
 - e. Eating disorder (current or within the past year).
 - f. Obsessive compulsive disorder (lifetime).
 - g. Post-traumatic stress disorder (current or within the past year).
 - h. ADHD (currently being treated).
3. Subjects meeting criteria for Axis II cluster A or B diagnosis based upon DSM-IV TR criteria, which in the judgment of the Investigator may hinder the subjects in completing the procedures required by the study protocol.
4. Subjects with a clinically defined neurological disorder including, but not limited to:
 - a. Any condition likely to be associated with increased intracranial pressure.
 - b. Space occupying brain lesion.
 - c. Any history of seizure EXCEPT those therapeutically induced by ECT (childhood febrile seizures are acceptable and these subjects may be included in the study).
 - d. History of stroke.
 - e. Transient ischemic attack within two years.
 - f. Cerebral aneurysm.
 - g. Dementia.
 - h. Mini Mental Status Exam (MMSE-2) score of ≤ 24 .
 - i. Parkinson's disease.
 - j. Huntington's disease.
 - k. Multiple sclerosis.
 - l. Increased risk of seizure for any reason, including prior diagnosis of increased intracranial pressure (such as after large infarctions or trauma), or currently taking medication that lowers the seizure threshold. Medications that lower the seizure threshold are included in the Prohibited Concomitant Medication (Section 5.8).
 - m. Any history of traumatic brain injury with loss of consciousness ≥ 30 minutes
5. Subjects who are currently hospitalized due to severity of depression symptoms.
6. Subjects with any of the following treatment histories:
 - a. TMS treatment within 6 months prior to the screening visit.
 - b. Lifetime history of treatment with sTMS therapy.

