The Columbia Suicide Severity Rating Scale is an easy-to-administer yet comprehensive measure that assists with the tracking of such thoughts, from a wish to die to an actual plan, and behaviors, from preparing for an attempt to an actual attempt. This scale will be administered at specific time points in the trial. Additionally, if a subject reports a new Adverse Event of depression worsening, suicidal ideation or suicide attempt at any time during the trial, a C-SSRS will be completed and appropriate actions should be taken to ensure the safety of the subject.
14. **Adverse Events:** Screening, Baseline, Week 1-6 Treatment and Evaluation Visits, Open Label Week 7-12 Treatment and Evaluation Visits
All adverse events, including the following, will be assessed by the Investigator, and recorded in the subjects study chart and on the appropriate case report form pages.
15. **Concomitant Medications:** Baseline, Week 1-6 Treatment and Evaluation Visits, Open Label Week 7-12 Treatment and Evaluation Visits
All medications prescribed and/or taken by the subject will be collected.
Any changes to these medications may be updated at any visit.
16. **Verification of Blinding Questionnaire:** Week 1 and 6 Evaluation Visits

Each subject, sTMS Administrator, and Rater will be asked to guess whether they believe the subject was randomized to active treatment or sham group. In addition they will be asked to provide a reason why they believe that they were randomized to the group they chose and their confidence level. Assessment of these data will be summarized at the completion of the trial.

17. Laboratory Assessments: Screening (Optional)

If the Investigator believes there is a need to assess a subject's safety for participating in the study based on the subject's history prior to enrolling, he/she may conduct blood tests for review prior to initiation of study treatments.

18. Physical Exam: Screening(Optional)

Physical exams may be done if the study physician feels it is indicated (e.g. because of medical history). This exam may include neurological assessments if applicable.

19. Electrocardiogram (ECG): Screening (Optional)

Electrocardiograms may be performed at Screening if the study physician feels it is warranted based on the subject's medical history or physical exam.

A flowchart of all study procedures can be found in Appendix I.

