9.3 REPORTING OF SERIOUS ADVERSE EVENTS AND UNANTICIPATED ADVERSE DEVICE EFFECTS

All Serious Adverse Events (SAE) and Unanticipated Adverse Device Effects that occur during the study, including death, must be reported within one working day by telephone to the study's Medical Monitor, and followed up in writing within 24 hours. The urgency for reporting SAE is four-fold: (1) to facilitate discussion (and implementation, if necessary) by the Sponsor and the Investigator of appropriate follow-up measures; (2) to facilitate Investigator reporting of unanticipated problems involving risk to human subjects to the IRB; (3) to facilitate the Sponsor's rapid dissemination of information regarding AEs to other Investigators/sites in a multi-center study; and (4) to enable the Sponsor to fulfill the reporting requirements to the appropriate regulatory authority. Serious adverse events should be reported by phone and facsimile to NeoSync, Inc.

Within the following 48 hours, the Investigator must provide further information on the serious adverse event or the unanticipated problem in the form of a written narrative. This should include a copy of the completed Serious Adverse Event form, and any other diagnostic information that will assist the understanding of the event. Significant new information on ongoing serious adverse events should be provided promptly to the study Sponsor.

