11.6 SAFETY DATA

The assessment of safety will be based mainly on the frequency of adverse events recorded. Other safety data (e.g., vital signs and ECG) will not be collected systematically but will be considered as appropriate. All safety analyses will be performed on the Safety Population as defined above.

Adverse events will be summarized by presenting the number and percentage of subjects having any treatment emergent adverse event (TEAE; defined as an AE that started or worsened in severity following randomized treatment), and having any TEAE within each MedDRA system organ class and within each MedDRA preferred term. Patients with multiple occurrence of an event will be counted once within the given system organ class and preferred term. This analysis will be repeated for serious TEAEs. TEAEs will further be categorized for each individual AE by severity and relationship to study treatment.

The incidence of treatment-emergent adverse events by MedDRA system organ classes and preferred terms will be compared between active and sham treatment using Fisher's Exact test.

Other information collected will be listed as appropriate.

Statistical tests performed on safety data to explore the data will be used only to highlight any interesting comparisons that may warrant further consideration. Safety summaries will be performed for each of the active and sham treatment for all study subjects in the Safety Population.

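### The SAE definition has no criterion for medically important events, so some seizures and suicide attempts would be classed as non-serious and miss expedited reporting and the serious-event tables

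*Protocol*

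**What the plan says.** Protocol Section 9 states: "A Serious Adverse Event (SAE) is defined as an adverse event that results in any of the following outcomes". The list that follows has five entries: death; "Is life-threatening"; hospitalization or its prolongation; "Persistent or significant disability/incapacity"; and congenital anomaly or birth defect. The UADE definition comes next. It covers unanticipated serious effects or problems associated with the device and does not require admission. A residual rule then applies: "All adverse events that do not meet any of the criteria for SAEs or UADEs should be regarded as non-serious adverse events". The same section says that progression of major depressive disorder is not to be treated as an SAE, while other events that meet the SAE criteria still count.

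The consequences of the classification are set elsewhere:

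- Protocol 9.3: SAEs and UADEs "must be reported within one working day by telephone to the" study's Medical Monitor.
- Protocol 11.6, after describing the treatment-emergent adverse event (TEAE) summary: "This analysis will be repeated for serious TEAEs". SAP section J repeats its summary for serious events in the same way and gives no SAE definition of its own.
- Protocol 7.2, item 13: a C-SSRS is completed, with action to keep the subject safe, "if a subject reports a new Adverse Event of depression worsening, suicidal ideation or suicide attempt at any time during the trial". It says nothing about SAE status or an expedited report.
- Protocol 4.2: item 4l excludes "Increased risk of seizure for any reason, including prior diagnosis of increased intracranial pressure", item 4c excludes most seizure histories, and item 9 excludes acute suicide risk.

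**The concern.** An SAE definition built only on outcomes leaves out events that are grave in kind but end without any listed outcome. Two such events matter here. Suicide attempt is foreseeable in this population: current antidepressants are withdrawn before baseline, subjects are allocated 1:1 to sham, and Protocol 13.3 names suicide as a risk if untreated depression worsens. Seizure is a hazard that the eligibility criteria and the prohibited-medication list take care to avoid.

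Confirming safety is part of the primary objective in Protocol Section 2. Serious events are the part of the safety record that reaches the Medical Monitor quickly and that readers of the report look at first. If a site follows the definition as written and so records a suicide attempt as a routine adverse event, the Medical Monitor receives no expedited report and the serious-event table does not count it. Two sites could also classify the same event differently, depending on how each reads the word serious in the UADE definition.

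**Working it through.** No arithmetic applies. The check is to follow a seizure or suicide attempt through the definitions and see where it ends.

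**Is the missing criterion supplied elsewhere?** Protocol 9.1 asks for seriousness criteria to be recorded for each adverse event but lists none. Protocol 9.2 and 9.3 add none. Protocol 11.6 and SAP section J use the term serious without defining it. The five outcomes in Section 9 are therefore the only SAE criteria, and the residual rule makes the list exhaustive apart from UADEs.

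**Where does the event end?**

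| Circumstances | Class | One-working-day call (9.3) | Serious-TEAE table (11.6, SAP J) | All-TEAE tables |
|---|---|---|---|---|
| Fatal, life-threatening, disabling or admitted | SAE | Yes | Yes | Yes |
| None of these, but judged an unanticipated serious problem associated with the device | UADE | Yes | Not settled: neither document specifies a UADE table | Yes |
| None of these, and not judged a UADE | Non-serious | No | No | Yes |

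The gap is the third row.

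**How far does the UADE route narrow it?** It needs two judgements.

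- *Association with the device.* Under Protocol 9.1, an event is not related only if there is evidence of a definite other cause, and possibly related needs little more than timing. With treatment five days per treatment week, a new seizure would often be at least possibly related. Seizure is also absent from the earlier study's possibly related events in Protocol 13.2, so on the protocol text it could count as unanticipated. The Instructions for Use, which the definition also refers to, are not among the documents. A suicide attempt is more readily attributed to the depression.
- *Seriousness.* The UADE definition uses the word serious without explaining it. If it takes its meaning from the five outcomes, an event that failed those criteria fails here too. If it does not, the decision is left to each Investigator.

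The route may therefore catch some seizures and is unlikely to catch many suicide attempts.

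**Does the progression sentence matter?** Protocol 7.2 item 13 lists depression worsening and suicide attempt as separate adverse events, which suggests that an attempt is not merely progression. Section 9 does not say so, and a site could read the exemption as covering an attempt.

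**Is there another timely route?** None is documented. The items that Protocol 12.1 says are updated weekly are enrollment, discontinuations and completions. The SAP describes the data monitoring board only in connection with the sample-size re-estimation.

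**The case against.** A reader might infer that any seizure or suicide attempt without admission has to be recorded as non-serious. The documents do not support that. Admission is one of five criteria; the life-threatening and disability criteria apply without it. The residual rule itself exempts UADEs, which carry the same one-working-day report.

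A reader might also infer that such events would vanish from the safety record. They would not. Protocol 9.1 requires every adverse event to be recorded with severity, relationship and seriousness. Protocol 11.6 and SAP section J summarise all TEAEs by MedDRA term, severity and relationship, so a seizure or attempt after the start of treatment would be visible by arm. SAP section M lists all case report form data. The C-SSRS is given at every evaluation visit and again after a reported attempt. Its value as a safeguard for reporting is limited, however: Protocol 10.3 names C-SSRS change as a safety outcome, but SAP section J sets out no analysis of it.

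It can fairly be said, too, that seizure is not shown to be a leading risk of this device. Protocol Section 1 attributes seizure potential to conventional TMS, and Protocol 13.2 describes a weak field and lists no seizure. The eligibility exclusions concern baseline risk. Nor do the documents require every seizure and every attempt to be an SAE whatever the circumstances.

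These objections limit the point. They leave the third row of the table untouched, and a suicide attempt without a listed outcome falls in it most readily.

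**Conclusion.** The point holds in a bounded form. The SAE definition lacks a criterion for important medical events or events needing intervention, nothing else in either document supplies one, and the residual rule closes the list. A seizure or suicide attempt that is not fatal, life-threatening or disabling, does not lead to admission, and is not judged a UADE is classed as non-serious. It loses the one-working-day report and its place in the serious-TEAE tables, and it keeps its place in the all-TEAE tables.

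No number can be put on this: the documents give no rate for either event, and the share of cases that would escape as UADEs depends on Investigators' judgement and on Instructions for Use that are not available here. The conclusion assumes that sites apply Section 9 as written and that no SAE form or site manual outside these documents widens the definition. It is a worthwhile and inexpensive correction to safety reporting and does not affect the efficacy analysis.

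**What to change.** Make these changes in Protocol Section 9:

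1. Add a sixth SAE criterion: an important medical event that, in the Investigator's judgement, jeopardises the subject or needs intervention to prevent one of the listed outcomes. Name seizure and suicide attempt as examples to be assessed under it. This asks for an explicit judgement and does not make every such event serious automatically.
2. State that a suicide attempt is not exempt from SAE classification as progression of disease. This brings Section 9 into line with Protocol 7.2 item 13.

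The SAE form needs the matching entry. The serious-TEAE summaries in Protocol 11.6 and SAP section J then inherit the definition, and a cross-reference to Section 9 in SAP section J is enough.

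The cost is two sentences in the protocol, one form entry and a few more expedited reports. Sample size, endpoints and the efficacy analysis are unchanged.

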9.1 ADVERSE EVENT ASSESSMENT

All adverse events, including the following, will be assessed by the Investigator via interview, and recorded in the subjects study chart and on the appropriate case report form pages.

- Observed or volunteered problems
- Complaints
- Physical signs and symptoms
- Medical condition which emerges during the study, having been absent at baseline
- Medical condition present at baseline, which appears to worsen during the study

The need to capture AEs is not dependent upon whether or not the clinical event is associated with the use of the investigational product.

Each AE must be described as follows: the date of onset, date of resolution, severity, frequency of the event (single episode, intermittent, continuous), action taken (none, medical and/or surgical), relationship to investigational device, and seriousness criteria must be recorded. Each adverse event must be recorded separately.

Severity will be assessed using the following definitions:

Mild	Aware of sign or symptom, but easily tolerated
Moderate	Discomfort enough to cause interference with usual activity
Severe	Incapacitating with inability to work or do usual activity

The relationship to investigational device will be assessed by the Investigator using the following definitions:

Not Related	Evidence exists that the adverse event definitely has a cause other than the investigational device (e.g. pre-existing condition or underlying disease, intercurrent illness, or concomitant medication) and does not meet any other criteria listed.
Possibly Related	A temporal relationship exists between the event onset and administration of investigational device. Although the adverse event may appear unlikely to be related to the investigational device, it cannot be ruled out with certainty; and or the event cannot be readily explained by the subject's clinical state or concomitant therapies.
Probably Related	A temporal relationship exists between the event onset and administration of investigational device, and appears with some degree of certainty to be related based on known therapeutic and pharmacologic actions of the investigational device. It cannot be readily explained by the subject's clinical state or concomitant therapies.

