13 RISK/BENEFITS

13.1 RESEARCH RISKS

Risks associated with participation in this trial include possible lack of positive response to the treatment or worsening of depressive symptoms. There is no guarantee that the treatment will lead to improvement in all subjects.

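### The exemption of MDD progression from SAE status has no limit by outcome, so worsening depression that itself meets a seriousness criterion is both an SAE and exempt from being one

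*Protocol*

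**What the plan says.** Protocol Section 9 lists the outcomes that make an adverse event serious. Two of them are "Is life-threatening" and "Requires in-subject hospitalization or prolongation of existing hospitalization"; death, persistent or significant disability and congenital anomaly complete the list. Events that meet none of the SAE or UADE criteria are to be regarded as non-serious.

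The same section then sets an exemption: progression of major depressive disorder "reflects lack of therapeutic efficacy and should not be treated as serious adverse events". The sentence after it reads, in part, "However, other events or complications meeting the criteria for serious adverse events should be considered as a serious adverse event", and asks for immediate reporting of those events whatever their presumed relationship to the device.

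Other sections deal with the same clinical event:

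- Section 9.1 includes in the adverse events to be recorded a "Medical condition present at baseline, which appears to worsen during the study", and requires seriousness to be recorded for each adverse event.
- Section 7.2 (C-SSRS) requires an extra C-SSRS "if a subject reports a new Adverse Event of depression worsening, suicidal ideation or suicide attempt at any time during the trial".
- Section 13.1 names "worsening of depressive symptoms" among the research risks.
- Section 9.3 requires SAEs, including deaths, to be telephoned to the Medical Monitor within one working day.
- Protocol 11.6 and SAP section J repeat the adverse event tables for serious treatment-emergent events.

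**The concern.** Confirming safety is part of the primary objective. Subjects stop antidepressants before baseline where they are taking them, and are then randomised 1:1 to active or sham treatment for six weeks. Serious worsening of depression can occur in either arm, and it is a harm on which the arms should be compared using one definition.

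The exemption carries no condition on outcome. Both the fast reporting route and the serious-event table accept only events already classed as serious. If a site follows the exemption literally, a psychiatric admission for worsening depression enters neither. If another site follows the outcome-based definition, the same kind of admission enters both. The serious-event comparison would then depend partly on how each site read Section 9.

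**Working it through.** The documents contain no figure on this point, so the check sets the rules side by side and follows one event through them.

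**Test event.** A subject's depression worsens during the double-blind phase and the worsening itself leads to hospital admission.

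| Rule | Result for this event |
|---|---|
| Section 9.1, worsening of a condition present at baseline | Adverse event; seriousness recorded |
| Section 9, SAE definition | Meets the hospitalisation criterion, so an SAE |
| Section 9, non-serious category | Does not fit, because a seriousness criterion is met |
| Section 9, progression exemption | Not an SAE |
| Section 9, sentence after the exemption | Does not clearly apply, because the admission arises from the progression and not from an *other* event |
| Section 9.3, one-working-day report | Depends on which rule above prevails |
| Protocol 11.6 and SAP section J, serious-event table | Depends on which rule above prevails |
| Protocol 11.6 and SAP section J, overall adverse event tables | Included either way |

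**Step 1: is there a conflict?** Yes. The second and fourth rows give opposite answers, and the third row shows that the non-serious category does not fit either. The same holds for worsening that is life-threatening or disabling.

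**Step 2: does the following sentence resolve it?** Not on its ordinary meaning. *Other* most naturally means other than progression. It restores complications and separate events, but it does not say that progression meeting a criterion regains SAE status.

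**Step 3: do the other sections settle it?** Section 7.2 and Section 13.1 do not. Calling worsening an adverse event, or a research risk, is compatible with exempting it from SAE status. Section 9.1 bears directly: it asks for seriousness to be recorded for an event that Section 9 says may not be serious.

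**Step 4: what recaptures the event if it is not classed as an SAE?** Only part of the information is recovered.

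- The overall treatment-emergent tables would contain it, by arm and by severity. The severity scale in Section 9.1 grades tolerability and interference with activity, so an admission is not separated from other severe worsening.
- The UADE route covers only unanticipated events tied to the device.
- C-SSRS change is a safety outcome in Protocol 10.3, but SAP section J describes no summary of it.

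**The case against.** The strongest reply is that a specific exception placed after a general definition is normal drafting, and that little is lost.

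Much of this stands. The exemption removes SAE status only. Section 9.1 keeps worsening as an adverse event with severity and seriousness recorded. Protocol 11.6 compares treatment-emergent events between arms with Fisher's exact test. SAP section A gives discontinuation reasons by arm, SAP section I compares HAM-D and MADRS at each time point, and SAP section M lists all CRF data. A reader might infer that the arms could not be compared on worsening at all; these provisions show otherwise.

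A reader might also infer that suicide attempts and deaths drop out. The text does not support that. Section 7.2 names suicide attempt separately from depression worsening, so an attempt can reasonably count as an *other* event, and Section 9.3 expressly includes death.

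Finally, a reader might want a count. Assuming that 2% to 5% of 120 subjects are admitted gives 120 × 0.02 = 2.4 to 120 × 0.05 = 6. The documents supply no such rate, and Section 4.2 excludes people currently hospitalised for depression severity or at significant acute suicide risk. Any such events would still be recorded as adverse events, so it would be wrong to call them unreported.

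The reply does not settle how to classify worsening that itself meets a criterion. Progression is not defined, and one could argue that an admission is a complication of it. That argument is available to one site and not binding on another, which is the difficulty.

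**Conclusion.** The point holds in a narrow form. Section 9 gives two incompatible classifications for worsening depression that itself leads to hospitalisation, is life-threatening or is disabling, and Section 9.1 adds to the conflict. Such events could be left out of one-working-day reporting and the serious treatment-emergent tables, or be classified differently across sites. Whether they are left out depends on how sites and the sponsor read the exemption, so omission is a possibility and not an established result.

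What is at stake is fast reporting and a correct serious-event table by arm. Basic capture of worsening is not in doubt. The conclusion rests on the wording alone, with *other events* given its ordinary meaning; it needs no assumed event rate, and none is claimed. This is an error in the text as written and should be corrected.

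**What to change.** Reconcile Sections 9 and 9.1. Limit the exemption to worsening of depression that meets none of the seriousness criteria listed in Section 9. State that worsening which meets any of them is an SAE, is reported under Section 9.3, and is counted by arm in the serious treatment-emergent table in Protocol 11.6 and SAP section J. The change concerns how events are classified and reported and alters no clinical management.

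The cost is one sentence in the protocol, a matching line in the SAP, and a few more SAE forms for sites and the Medical Monitor. If subjects have already been enrolled, adverse events of worsening depression recorded so far should be reviewed against the revised wording while treatment assignment is still blinded.
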